Official Title of the study:

**Effect of Dexamethasone on Reduction of Macular Thickness in
Diabetic Patients, a Randomized Clinical Trial**

NCT number

NCT03608839

Date of the document

October 2, 2019

Study Protocol:

Data from DME diagnosed volunteers was collected and analyzed at the Department of Ophthalmology, State University of Campinas (UNICAMP), Brazil between May 2016 and December 2017.

Inclusion criteria included: (1) aged 18 years or over; (2) diagnosis of Type 2 DM; (3) patients with pseudophakic eyes; (4) presence of clinically significant DME according to ETDRS guidelines; (5) best corrected visual acuity (BCVA) between 20/400 and 20/40; (5) central macular thickness (CMT) of $\geq 300 \mu\text{m}$, measured by spectral domain optical coherence tomography (Spectralis® Heidelberg). If both eyes met eligibility criteria, the eye with worse BCVA at baseline was used as the study eye.

Exclusion criteria were: (1) any treatment of DME in the previous 4 months; (2) pan retinal photocoagulation (PRP) in the last 4 months or likelihood of necessity to undergo PRP during the next 6 months; (3) any ophthalmologic surgery performed in the last 4 months; (4) history of pars plana vitrectomy (PPV); (5) history of open-angle glaucoma or corticosteroid-induced elevated intraocular pressure that required antiglaucoma or anti-hypertensive ocular treatments; (6) intraocular pressure of $\geq 21 \text{ mmHg}$; (7) patients that refused to sign the informed consent form.

During the screening consultation, complete ophthalmic evaluation, including BCVA, slit-lamp biomicroscopy, applanation tonometry, fundus biomicroscopy, fluorescein angiography (Visucam NM/ FA Carl Zeiss; Carl Zeiss Meditec, California, USA) and SD-OCT (Spectralis; Heidelberg Engineering, Heidelberg, Germany) was performed. CMT was obtained through seven horizontal lines ($30^\circ \times 5^\circ$ area), centered on the fovea, with 1536 A scans per line at $240 \mu\text{m}$ intervals.

Patients were randomized via a 1:1:1 sequential allocation to receive 0.01 ml ($40\mu\text{g}$), 0.03 ml ($120\mu\text{g}$), or 0.05 ml ($200\mu\text{g}$) of the 4mg/ml dexamethasone solution during the primary study visit (baseline). In subsequent visits, at one, three, seven, 14, 21, and 28 days, analysis via BCVA, slit-lamp biomicroscopy, applanation tonometry, fundus biomicroscopy, and SD-OCT (Spectralis; Heidelberg Engineering, Heidelberg, Germany) was performed.

The current study used blocked randomization (3 groups with 9 members each); data was computer generated, and stored in a locked cabinet until the end of the study period. Patients, study personnel responsible for intravitreal injections and those responsible for collecting BCVA, IOP, OCT data were blinded as to the patient study assignment.

Statistical Analysis Plan:

Calculations based on effect size at 0.5 standard deviations of macular thickness between pre injection (baseline) and the 3rd day post injection indicated that a sample size consisting 27 subjects would be sufficient for detecting a difference of this magnitude with a power of 0.8 and a significance level of 0.05 (one-tailed).

In statistical analysis, continuous data were expressed as the mean \pm standard deviation and range. Between-group differences of continuous variables were compared using Kruskal-Wallis 1-way ANOVA, Wilcoxon Signed Ranks Test or Mann-Whitney U test when appropriate, and categorical variables were compared using or Fisher – Freeman – Halton exact test. Analyses were performed using IBM SPSS Statistics version 20. Statistical significance was established when $p \leq 0.05$.

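### Does the missing description of how injection volume was hidden from the masked injectors call for a change to the plan?

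*Combined protocol and SAP*

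**What the plan says.** The Study Protocol section says patients were "randomized via a 1:1:1 sequential allocation to receive 0.01 ml", with 0.03 ml and 0.05 ml as the other two arms, all drawn from the same "4mg/ml dexamethasone solution during the primary study visit (baseline" visit. One injection is described, followed by assessments from day 1 to day 28.

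The closing paragraph of that section describes "blocked randomization (3 groups with 9 members each") with a computer-generated sequence that was "stored in a locked cabinet until the end of the study period". It then states who was masked: "Patients, study personnel responsible for intravitreal injections and those responsible for collecting BCVA, IOP, OCT data were blinded as to the patient study assignment". It gives no detail on preparing, handing over or shielding the syringes, and no block size apart from the group totals.

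The Statistical Analysis Plan section sizes the trial on the change in macular thickness from baseline to day 3. For comparisons between arms it says: "Between-group differences of continuous variables were compared using Kruskal-Wallis 1-way ANOVA", with other rank tests where appropriate. It mentions no baseline adjustment.

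**The concern.** Someone giving an intravitreal injection would ordinarily see how much is in the syringe. Here that amount is the assignment, over a five-fold range (0.05 / 0.01 = 5). A claim that the injector was masked therefore invites the question of how. The locked cabinet does not answer it, because it protects the list and not the syringe.

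The possible consequence is for allocation concealment. Group totals are fixed at 9, 9 and 9, so anyone who knew the earlier assignments could partly predict the later ones without opening the cabinet. Most entry criteria are measurements or history, but one exclusion turns on a forward-looking judgement, "likelihood of necessity to undergo PRP during the next 6 months". A predicted arm could sway that judgement at enrolment. With nine patients per arm and no baseline adjustment, a few selectively enrolled patients could shift a between-dose comparison.

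**Working it through.** **1. Are the arms separated by volume alone?** Inputs: volumes and concentration from the Study Protocol section. Dose = volume × concentration, and 4 mg/ml is 4,000 µg/ml.

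- 0.01 × 4,000 = 40 µg
- 0.03 × 4,000 = 120 µg
- 0.05 × 4,000 = 200 µg

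All three match the stated doses. Concentration is constant, so volume is the only distinguishing feature described.

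**2. Which comparison was the trial sized for?** Inputs from the Statistical Analysis Plan section: effect 0.5 SD, one-tailed 5% level, power 0.8. For a paired t-test on n patients the noncentrality is 0.5 × √n. At n = 27 it is 0.5 × 5.196 = 2.598 and the power is 0.812; 27 is the smallest n that reaches 0.80. The stated 27 is thus reproduced as a within-patient change over all patients together. That contrast does not compare doses, so knowledge of which dose a patient received does not bear on it in the way it would on a between-arm test.

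**3. How predictable could later assignments be?** Input from the document: 9 per arm, 27 in all. Assumptions not in the document: the observer saw every earlier volume, knew the block structure, and always guessed the arm with most places left. For a block of size B, expected correct guesses are the sum over r = 1 to B of E[largest remaining count] / r, where r is the number of places left. With k places per arm in the block, the expected number of assignments known with certainty (only one arm left) is B / (B − k + 1).

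| Structure | Correct of 27 | Known for certain |
|---|---|---|
| Volume hidden | 27 / 3 = 9.0 | 0 |
| One block of 27 (k = 9) | 12.49 | 27 / 19 = 1.42 |
| Three blocks of 9 (k = 3) | 14.36 | 3 × 9/7 = 3.86 |
| Nine blocks of 3 (k = 1) | 9 × (1/3 + 1/2 + 1) = 16.5 | 9 × 1 = 9.0 |

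Only the 9/9/9 totals are documented. On those alone the excess over chance is 12.49 − 9.0 = 3.49 guesses. The last two rows need block sizes that the document does not give.

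**4. What must hold before a guess becomes bias?** All of the following: volume was visible to the injector; that person kept track of earlier volumes; they knew the block structure; they took part in enrolment; and they let the guess affect an eligibility judgement. The document states none of these. If injecting and enrolling staff were different people who did not share what they saw, the effect on enrolment is nil whatever the block size.

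**5. Do the statements conflict?** The list was locked away until the study ended and the injectors are said to be masked. Both can be true if someone else drew up each dose, if the syringe was shielded, or if total volume was equalised. The text does not say which, but it is not contradictory.

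**The case for a change.** The best case for acting is that brevity does not fully excuse the silence. The document does give concealment details (computer generation, locked cabinet) and it goes out of its way to name the injectors as masked. That is the one claim a reader will doubt when the arm is the injected volume. The text also leaves open how each assignment reached whoever drew up the dose while the list was locked. Stating the procedure would cost a few sentences, and if no procedure could be documented, the masking claim should cover only patients and those collecting BCVA, IOP and OCT data.

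Part of this stands. A reader cannot verify the injector claim from the document, and a sentence on syringe preparation would be useful when the trial is reported. What does not stand is the step from silence to a defect. Silence in so short a text, written in the past tense and dated October 2019 about data collected from May 2016 to December 2017, is weak evidence about conduct. The prediction figures count correct guesses by a hypothetical observer; they do not measure bias in macular thickness, acuity or pressure. The lack of baseline adjustment is a separate choice of analysis and not a masking matter.

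**Conclusion.** No change to the plan follows. The observation is accurate: arms that differ only in volume, injectors said to be masked, no mechanism given. It is a reporting gap. A trial run as the document states, with injectors masked, gives sound comparisons, and filling the gap alters no test, sample size or analysis.

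The outcome path is also protected as written. Those collecting BCVA, IOP and OCT data are named separately from the injectors and stated to be masked, macular thickness is an SD-OCT measurement, and the sized contrast is baseline to day 3 rather than dose against dose.

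At most, if volume was visible and the same staff enrolled patients, the fixed 9/9/9 totals would yield about 3.5 extra correct guesses in 27 and about 1.4 certain ones; smaller blocks, if used, would yield more. Failure of masking, predictable allocation and bias are not shown. This conclusion takes the masking statement at face value; records showing that injectors could see the volume and also enrolled patients would reopen the question for the between-dose comparisons.

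### Does the analysis rule p ≤ 0.05, which states no tail, undo the one-tailed 80% power claimed for 27 patients?

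*Combined protocol and SAP*

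**What the plan says.** The sample-size paragraph of the Statistical Analysis Plan starts from "effect size at 0.5 standard deviations of macular thickness between pre injection (baseline) and the 3rd day post injection" and concludes that "a sample size consisting 27 subjects would be sufficient for detecting a difference of this magnitude". It attaches these conditions: "with a power of 0.8 and a significance level of 0.05 (one-tailed". The tail is thus stated openly for the contrast on which the trial was sized.

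The analysis paragraph then lists the tests: "Between-group differences of continuous variables were compared using Kruskal-Wallis 1-way ANOVA, Wilcoxon Signed Ranks Test or Mann-Whitney U test when appropriate", with a Fisher–Freeman–Halton exact test for categorical variables. It ends with one rule: "Statistical significance was established when" p ≤ 0.05. It gives no tail, does not mention day 3, and does not say which listed test serves the powered contrast.

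The Study Protocol describes three dose groups and follow-up at six visits. Its blinding sentence shows that visual acuity and intraocular pressure are collected as well as OCT data ("those responsible for collecting BCVA, IOP, OCT data were blinded").

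**The concern.** The stated power depends on the tail, because 27 is the smallest sample that reaches 80% for a one-tailed paired t-test at 0.5 SD. The single significance rule also covers Kruskal-Wallis and the Fisher–Freeman–Halton test, which have no direction, and outcomes for which the plan gives none. A reader may infer that p ≤ 0.05 is meant as two-sided throughout and that the one-tailed test used for sizing was dropped.

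Two things would then be at stake. The power would be about 0.70, not 0.8. The same day-3 data could also be called significant or not, depending on a tail that the analysis paragraph leaves unstated. With no true change, the chance of declaring a reduction is 5% under a one-tailed rule and 2.5% under a two-sided one.

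**Working it through.** **Inputs from the Statistical Analysis Plan:** effect 0.5 SD, n = 27, α = 0.05 one-tailed, target power 0.8.

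**Assumptions, not in the text:** the test is paired, all three groups are pooled (3 × 9 = 27), and the SD is that of the within-patient change. This reading is adopted because it reproduces 27.

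**1. The plan's own figure.** For a paired t-test with d = 0.5, the noncentrality is d√n = 0.5 × √27 = 2.598 on 26 df. One-tailed power is the probability that this noncentral t exceeds t(0.95; 26).

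- n = 26: 0.798
- n = 27: 0.812

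So 27 is the one-tailed minimum, and the calculation is right. Two independent means would need 50 per arm one-tailed, which cannot give 27.

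**2. The same test under either tail.**

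| Test | n = 27, one-tailed | n = 27, two-sided | Smallest n for 80%, two-sided |
|---|---|---|---|
| Paired t | 0.812 | 0.706 | 34 (0.808; n = 33 gives 0.795) |
| Signed-rank | 0.789 | 0.685 | 35 (0.801; n = 34 gives 0.787) |

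The signed-rank values come from the exact test in 400,000 simulated normal samples. The cost of the tail is 0.812 − 0.706 = 0.106 for the t-test and 0.789 − 0.685 = 0.104 for the signed-rank test. The fall from the stated 0.8 to 0.685 therefore has two parts. About 0.10 is the tail. The remaining 0.01 or so (0.80 to 0.789) comes from using a rank test, which needs 28 patients for 80% even one-tailed (power 0.808).

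**3. Where the two readings give different answers (t-test).** The critical observed reduction is t/√27:

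- one-tailed: t(0.95; 26)/√27 = 0.328 SD of the change
- two-sided: t(0.975; 26)/√27 = 0.396 SD of the change

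At a true 0.5 SD, 10.6% of trials fall between these limits.

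**4. Sensitivity to the SD.** If 0.5 refers to the SD of thickness itself, then d = 0.5/√(2(1 − r)), where r is the baseline-to-day-3 correlation. The document does not give r, so the values below are assumed.

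| r | Two-sided power, n = 27 | One-tailed power, n = 27 | Smallest one-tailed n for 80% |
|---|---|---|---|
| 0.3 | 0.561 | 0.689 | 37 |
| 0.5 | 0.706 | 0.812 | 27 |
| 0.7 | 0.898 | 0.947 | 17 |

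Only r near 0.5 is consistent with 27 as the calculated result.

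**5. Do the two paragraphs contradict each other?** The first gives level 0.05, one-tailed, for the day-3 change. The second gives a threshold of 0.05 for whatever p-value a test yields. A one-tailed p from the day-3 test and a p from an omnibus test with no direction can both be held against 0.05. That Kruskal-Wallis has no tail says nothing about the tail of a paired test. Every two-sided figure above therefore depends on a choice that appears nowhere in the document.

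**The case for a change.** The strongest case for a change is that the tail is disclosed for sizing only. The analysis paragraph is where a test is specified, and it carries over neither day 3, nor the direction, nor the tail. The power claim sits right at its one-tailed minimum, so this silence affects the only contrast the trial was sized on. One sentence would settle it, and a two-sided p with a 95% confidence interval for the day-3 change would let any reader recognise a one-tailed p between 0.025 and 0.05.

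Much of this stands. The arithmetic is correct, the analysis paragraph is thin, and such an interval would be useful to a reader of the results. What does not stand is the step from silence to mismatch. The added sentence would only repeat what the sample-size paragraph already implies, in a title that already names reduction of macular thickness as the effect sought. Restating the power would be right only if the test had in fact been two-sided. The extra p-value and interval are a reporting preference and correct no figure or rule in the plan. The Study Protocol also says the data were collected and analysed between May 2016 and December 2017, and the document is dated October 2019. A tail written in now could not alter the sample size and could be taken for one chosen after the results were known.

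**Conclusion.** No change to the plan follows. The figure of 27 is correctly derived and its tail is openly stated. At the stated level and tail, the design gives 0.81 by paired t or 0.79 by signed-rank, in line with the claimed 0.8; the 0.01 shortfall with the rank test is immaterial. Power of 0.71 or 0.685, and a requirement of 34 or 35 patients, would apply only if the day-3 test was run two-sided, and nothing in the document says so.

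What remains is a missing detail: the analysis paragraph does not repeat the tail or name the day-3 test. The sensible way to fill it is to confine the one-tailed level to the day-3 reduction and treat other directional tests as two-sided.

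This conclusion assumes a paired, pooled test with 0.5 in SDs of the change; the signed-rank figures also assume normally distributed changes. It does not bear on power to compare the three doses.

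### IOP is covered only by generic group summaries and rank tests, which with 9 eyes per arm have little ability to detect a marked rise in 2 to 4 eyes; a per-eye IOP table by dose is needed

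*Combined protocol and SAP*

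**What the plan says.** The Study Protocol section compares three dexamethasone doses given by intravitreal injection, randomised 1:1:1, and schedules tonometry repeatedly: "In subsequent visits, at one, three, seven, 14, 21, and 28 days, analysis via BCVA, slit-lamp biomicroscopy, applanation tonometry". The randomisation paragraph gives "blocked randomization (3 groups with 9 members each" and lists IOP with the other blinded measurements: "those responsible for collecting BCVA, IOP, OCT data were blinded". At entry, eyes at 21 mmHg or above are excluded, as are patients with "history of open-angle glaucoma or corticosteroid-induced elevated intraocular pressure that required antiglaucoma or anti-hypertensive ocular treatments".

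The Statistical Analysis Plan does not name IOP. As a continuous variable, IOP falls under its general rule: "continuous data were expressed as the mean \pm standard deviation and range. Between-group differences of continuous variables were compared using Kruskal-Wallis 1-way ANOVA", or the Wilcoxon signed-rank or Mann-Whitney test where suitable. A Fisher-Freeman-Halton exact test is planned for categorical variables, but no IOP category is defined. The documents contain no per-eye peak, no change from baseline, no count of eyes with a rise, no rule for eyes given pressure-lowering treatment, and no adverse-event analysis.

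**The concern.** A pressure response to a steroid occurs in individual eyes. Some eyes respond, possibly at different visits, and the rest do not. The entry criteria already treat it this way, through a threshold and a history of response in the individual patient. The analysis rule instead summarises and compares whole groups, visit by visit. A few large rises are then diluted by the non-responders in the arm and, if brief, by the visits at which the eye reads normal.

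A dose comparison invites a statement about whether higher doses raise pressure. Under the plan as written, that statement could be that IOP did not differ between doses, even if a third of one arm had a marked rise, and no planned table would show how many eyes were affected.

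**Working it through.** **The plan's own figure.** The sample size rests on an "effect size at 0.5 standard deviations of macular thickness between pre injection (baseline) and the 3rd day post injection", one-sided alpha 0.05 and power 0.8, and concludes that "a sample size consisting 27 subjects would be sufficient". A paired one-sided t-test with d = 0.5 gives power 0.812 at n = 27, so the figure reproduces. It concerns macular thickness in all patients together and says nothing about IOP between arms of 9.

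**1. Rank tests at one visit, by hand.** Suppose k eyes in one arm hold the top k of 27 ranks and all other eyes share the average of the remaining ranks, (28 − k)/2. The Kruskal-Wallis statistic is H = [12/(27 × 28)] × 9 × Σ(mean rank − 14)², and on 2 df p = exp(−H/2).

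| k | Mean rank, affected arm | Mean rank, other arms | H | p |
|---|---|---|---|---|
| 2 | 16 | 13 | 0.86 | 0.65 |
| 3 | 17 | 12.5 | 1.93 | 0.38 |
| 4 | 18 | 12 | 3.43 | 0.18 |
| 6 | 20 | 11 | 7.71 | 0.02 |

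The size of the rise does not matter once the eyes hold the top ranks.

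The alternatives behave similarly under the same device:
- Mann-Whitney, 9 against 9: z = 4.5k/√(9 × 9 × 19/12) = 4.5k/11.3. Two-sided p is 0.43, 0.23 and 0.11 for k = 2, 3, 4.
- Signed-rank within the arm: the SD of the rank sum is √(9 × 10 × 19/24) = 8.44, and the excesses over 22.5 are 8.5, 12 and 15. Two-sided p is 0.31, 0.16 and 0.08.

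The analysis paragraph does not state sidedness. One-sided values are half of these, so only the signed-rank test with k = 4 would fall below 0.05.

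**2. Simulation.** From the documents: 3 arms of 9 and six visits. Assumed, because the documents give no IOP figures: SD of change 2.5 mmHg, and a rise of 15 mmHg in k eyes of one arm.

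| Eyes affected, of 9 | Brief: one random visit after day 1 | Sustained from day 7, at an affected visit |
|---|---|---|
| 2 | about 4-5% | about 8% |
| 3 | about 4-5% | about 15% |
| 4 | about 4-5% | about 28% |

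These are Kruskal-Wallis rejection rates per visit. With no rise the rate is also about 4-5%. A separate simulation (between-eye SD 2.5, within-eye SD 1.5, rises of 10 or 15 mmHg in 0/1/3 eyes of the low/middle/high dose at different visits) gave 4.6%, against 4.3-4.9% with no rise. Varying the SDs (between-eye 1.5-3.5, within-eye 1-2) left it at about 4.7-4.8%.

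**3. Group means.** For 3 of 9 eyes with one brief 15 mmHg rise, the arm mean over six visits moves by (3/9) × (15/6) = 0.83 mmHg.

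**4. Per-eye counts.** In the brief-rise simulation, counting eyes whose largest rise reaches 10 mmHg (an illustrative cut) recovers on average 1.96, 2.93 and 3.91 of the 2, 3 and 4 affected eyes. The exact Fisher-Freeman-Halton p-values for such counts are:
- 0/0/2: 3 × C(9,2)/C(27,2) = 108/351 = 0.31
- 0/0/3: 3 × C(9,3)/C(27,3) = 252/2925 = 0.086
- 0/0/4: 3 × C(9,4)/C(27,4) = 378/17550 = 0.02
- 0/1/3: (378 + 6 × 9 × 84)/17550 = 4914/17550 = 0.28

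**5. What zero events would mean.** The exact two-sided 95% upper limit for 0 of n is 1 − 0.025^(1/n). This is 0.336 for n = 9 and 0.128 for n = 27. For 3 of 9 the interval is 7% to 70%.

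**The case against.** A reader might infer that the plan cannot see a pressure rise at all. It does not go that far: the quoted sentence also promises the range. In the simulation of brief rises, the affected arm's maximum change reached 10 mmHg in essentially every trial with 2 to 4 responders. If ranges are given by visit and dose, which the plan does not say, an extreme reading would be visible. This part of the objection stands. What the range leaves out is the number of eyes and, if raw IOP is tabulated, the change from baseline.

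A reader might also say that the tests are always no better than chance. That holds only for brief, scattered rises, and the documents describe no time course. With rises sustained from day 7, at least one of six visits is significant in about 34%, 52% and 76% of trials for 2, 3 and 4 eyes. That must be set against about 25% with no rise, because six unadjusted tests are made. Sensitivity is therefore low for 2 or 3 eyes but not nil.

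Nor do the documents call IOP the trial's safety measure or announce a conclusion about IOP safety. They define no endpoints. That role is a natural inference from the drug, the exclusions and the repeated tonometry, but it is still an inference.

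Finally, a count does not rescue the significance test: the exact test also misses 2 or 3 responders. Much of the difficulty is having 9 eyes per arm. The gain from counting is descriptive.

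**Conclusion.** The concern holds in a limited form. By default, IOP is analysed with methods that have little or no ability, at 9 eyes per arm, to detect a marked rise in 2 to 4 eyes: about 4-5% rejection per visit for brief, scattered rises and about 8-28% for rises sustained from day 7. These figures rest on an assumed SD of change of 2.5 mmHg and a 15 mmHg rise. The hand calculation on ranks needs neither and points the same way. The range is a partial safeguard. What is missing is a per-eye summary showing how many eyes rose, by how much and at which dose. This should be corrected before any statement on IOP by dose is made. It does not affect the macular-thickness analysis or the stated N of 27.

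**What to change.** Add one per-eye IOP table by dose arm, from the tonometry readings already collected, giving:
- peak IOP after injection;
- largest change from baseline, saying which reading is the baseline, since tonometry before injection is listed only at screening;
- number of eyes crossing a level at any visit, with exact 95% confidence intervals;
- individual listings of all readings.

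The trial team should set and justify the level. The 21 mmHg figure is an entry criterion; used as an outcome it would count an eye moving from 20 to 21. The 10 mmHg cut used above appears nowhere in the documents. Eyes given pressure-lowering treatment should count as events if that treatment was recorded, which the documents do not say.

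Present the table as descriptive and label it post hoc, because data collection ended in December 2017. Any Fisher-Freeman-Halton p-value is secondary. State that a non-significant test of IOP is not evidence of IOP safety, and that the results apply to eyes without previously treated glaucoma or treated steroid response.

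The cost is some SAP wording and one table, with no further visits or patients. The downside is that wide intervals make the safety statement less favourable.

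### Does the plan leave it open whether the baseline-to-day-3 signed-rank test pools all 27 patients or runs in each arm of 9?

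*Combined protocol and SAP*

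**What the plan says.** The sample size paragraph of the Statistical Analysis Plan bases its calculation on an "effect size at 0.5 standard deviations of macular thickness between pre injection (baseline) and the 3rd day post injection". It concludes that "a sample size consisting 27 subjects would be sufficient for detecting a difference of this magnitude". The same sentence ends by fixing the power at 0.8 and the significance level at 0.05, one-tailed.

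The randomization paragraph just before that heading describes "blocked randomization (3 groups with 9 members each"), so 27 is the whole trial.

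The analysis paragraph names the tests for continuous data in one sentence: "Between-group differences of continuous variables were compared using Kruskal-Wallis 1-way ANOVA, Wilcoxon Signed Ranks Test or Mann-Whitney U test when appropriate". It then sets the threshold at p ≤ 0.05, in the sentence beginning "Statistical significance was established when", without naming a tail. No sentence in that paragraph mentions within-patient change, day 3, or the patients on whom a pre/post test is run.

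**The concern.** The Wilcoxon signed-rank test is a paired test, and the three arms hold different patients, so it cannot compare arms. Its natural use here is the baseline-to-day-3 contrast, but the sentence that names it announces a different purpose. Taken alone, the analysis paragraph could be met by one test on 27 patients or by three tests on 9 patients each, and the second is a natural thing to do in a three-dose trial.

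The stated power of 0.8 would not carry over to tests in single arms. A reader might set a non-significant arm against a power it never had. With three unadjusted tests, the chance of at least one false-positive arm would also rise. The unstated tail of the p ≤ 0.05 rule adds a smaller uncertainty of the same kind.

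**Working it through.** **Inputs.** From the sample size paragraph: effect 0.5 SD, one-tailed α = 0.05, power 0.8, n = 27. From the randomization paragraph: 9 patients per arm. Assumption: the 0.5 SD is in units of the SD of the within-patient change, so the standardized paired effect is d = 0.5.

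**1. The plan's own figure.** The power of a one-tailed paired t-test is P(T > t₀.₉₅,ₙ₋₁), where T is noncentral t with n − 1 degrees of freedom and noncentrality d√n.

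- n = 27: noncentrality 0.5 × √27 = 2.598, critical value 1.706, power 0.812.
- n = 26: noncentrality 0.5 × √26 = 2.550, critical value 1.708, power 0.798.

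So 27 is the smallest n that reaches 0.8, and the stated figure reproduces exactly. The alternatives do not match: a two-sided paired t-test needs 34 patients, and a two-sample comparison at 0.5 SD needs 50 per arm one-sided or 63 two-sided (normal approximation).

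**2. The two readings at d = 0.5.** The signed-rank values use exact critical values and simulated normal changes.

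| Test | n = 27, one-tailed | n = 27, two-sided | n = 9, one-tailed | n = 9, two-sided |
|---|---|---|---|---|
| Paired t | 0.81 | 0.71 | 0.39 | 0.26 |
| Signed-rank | 0.79 | 0.69 | 0.38 | 0.22 |

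**3. False positives.** The exact one-tailed signed-rank test has size 0.0477 at n = 27 and 0.0488 at n = 9. Three independent per-arm tests give 1 − (1 − 0.0488)³ = 0.139. That figure supposes no effect in any arm and a rule that counts any one significant arm as success. The plan contains no such rule.

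**4. Sensitivity to the SD assumption.** The wording could mean the SD of raw thickness. With equal SDs at the two visits and baseline-to-day-3 correlation r, the paired effect is 0.5/√(2(1 − r)), which equals 0.5 only at r = 0.5. The documents give no r. One-tailed paired t power over a range:

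| r | Paired effect | n = 27 | n = 9 |
|---|---|---|---|
| 0.3 | 0.42 | 0.69 | 0.31 |
| 0.5 | 0.50 | 0.81 | 0.39 |
| 0.7 | 0.65 | 0.95 | 0.55 |
| 0.8 | 0.79 | 0.99 | 0.70 |
| 0.9 | 1.12 | about 1.00 | 0.92 |

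The exact match in step 1 favours the SD of the change, but that is an inference. The size of the gap between pooled and per-arm power depends on it.

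**5. The two paragraphs read together.** The sample size paragraph supplies the contrast, the 27 patients and the tail. The analysis paragraph supplies a list of tests, of which only the signed-rank test fits a paired contrast, and lets each be used where it is suitable. Together they lead to one pooled, one-tailed signed-rank test. The mention of groups of 9 describes how patients were allocated and gives no instruction for analysis.

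**The case for a change.** The strongest case for a change is that correcting the label alone would not settle the matter. Nothing in the document states outright which patients enter the pre/post test, and the analysis threshold carries no tail. The calculations hold for the inputs used, and two sentences of text would close the gap without new patients or data.

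All of that stands as a description of the text. It does not show that the plan is wrong. The sample size is right for the contrast it names, on the stated assumption about the SD. The tail is given once, for that contrast, and leaving it out of the next paragraph is not a contradiction. Reading the plan as three per-arm tests means setting aside the paragraph directly above, so the two readings are not equally supported.

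A rewrite also has a difficulty of its own. The Study Protocol's opening paragraph reports the work in the past tense, "Data from DME diagnosed volunteers was collected and analyzed at the Department of Ophthalmology", with an end date of December 2017, and the document is dated October 2019. Inserting pooled, one-tailed and exploratory labels now would pick among the options while presenting the choice as what had been planned, and the documents cannot confirm that it was. The most one could ask is that the sponsor say which test was intended, on which patients and with what tail.

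**Conclusion.** No change to the plan is called for. This is a gap that an analyst fills sensibly from the adjoining paragraph, together with a clerical slip in where the signed-rank test is listed. Running the test that was sized complies with the plan and has power of about 0.8 (0.81 by paired t, 0.79 by signed-rank). Writing down its population and tail would record a detail. It would neither replace a wrong rule nor bring in a better method.

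A reader of the results should keep one caution in mind: the stated power belongs to the pooled, one-tailed test. At 0.5 SD of the change it falls to about 0.39 (paired t) or 0.38 (signed-rank) within one arm, and to about 0.71 or 0.69 if the pooled test was two-sided. These values assume normal changes and an effect measured in SDs of the change. If the SD is that of raw thickness, per-arm paired t power runs from 0.31 to 0.92 for correlations from 0.3 to 0.9.
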